The study is a randomized, placebo controlled, double-blind parallel design with two treatment arms, each of approximately 2-3 weeks duration. In the 2-3 week treatment phase participants will start study drug and titrate up to the maximum tolerated or targeted dose (2.5 mg/kg/day of CBD). Each participant will have a screening visit, baseline visit within four weeks, 2 dose assessment visits (1.25 mg/kg/day and 2.5 mg/kg/day), and a safety visit (5 visits total). Participants will be evaluated at each dose level for monitoring adverse events, as well as changes in medical history and concomitant medications. Further, in case CBD alters the reliability of self - report, repeated measures will be taken on the third to fifth day at each dose during the clinic visits or at home. The assessments include the assessment of tolerability and symptoms of hepatotoxicity, SCOPA-sleep, Anxiety short form, Depression short form, Emotional and behavioral dyscontrol short form, and EQ-5D-5L. Participants are called 3 and 7 days after stopping the study drug to check for signs of withdrawal. At dose assessment visits, urinary CBD and metabolites will be tested. To maximize compliance the coordinator calls the participant to remind them the next day's clinical visit. To increase compliance with taking study drug, participants will be asked to fill out a diary at home. The diary will be a record of the date and time participants take study drug, dose of the study drug, and adverse and beneficial events. Study drug is dispensed at the baseline visit. Participants will measure their tremor using Tremor GUI MATLAB twice a day (two hours after breakfast dose and two hours after dinner dose) for two consecutive days after screening visit, three consecutive days prior to baseline and each dose assessment visit, as well as during the clinic visits. To evaluate the possible somnolence effect of CBD, participants will be evaluated their alertness before and three hours after they take the study drug at baseline visit.

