Visit 2- Baseline visit: Eligibility confirmation (including tremor evaluation), medical history, concomitant medications collection, formal drug interaction assessment, vital signs, orthostatic blood pressures, brief physical exam, MoCA, MDS-UPDRS, H&Y rating, UDysRS, NMSS, OABSS, tremor constancy and amplitude two hours after taking study drug, TUG test, cognitive assessment battery (including tests of verbal intellectual function, attention, processing speed, executive function, verbal learning and memory, visuospatial memory, speeded verbal fluency, and word retrieval), Anxiety short form, Depression short form, SCOPA-Sleep, ISI, DBAS-16, Pittsburgh Sleep Quality Index, Alertness test, RBDSQ, C-SSRS, IRLS, Fatigue severity scale, Pain intensity and interference short form, PDQ-39, EQ-5D, CGI, PGI, urine drug (THC) test (urine dipstick test), urine pregnancy test (women childbearing potential) and study drug dispensing is done and, if appropriate, randomization. Skin evaluation (Dermatology Intake Form, DLQI, and dermatology

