#### C.2 Study Drug: CBD:

The study drug is supplied by NIDA; see Appendix 4 for Certificate of Analysis (COA). The study drug (CBD) is provided in the form of a thick liquid and will be diluted into a 100 mg/ml formulation with sesame oil. This procedure will be done by the PharmDs ([name], [name], and [name] as a consultant) or PI, according to the protocol we develop with guidance from NIDA and the University of Mississippi researchers that produced the material. The placebo will be made by the study Pharm Ds from USP grade sesame oil and food coloring. Because the placebo may be slightly different in appearance or taste, two study modifications are being done to preserve the blind. First, the study drug will be put into brown opaque bottles and the only study personnel to see the actual study drug will be the unblinded PharmD and the blinded CTRC PA that instructs the subject on how to take study drug. Further, the study drug is administered in a closed, vented room in the CTRC that removes the odor of cannabis within four minutes. After the study drug is administered and the study drug bottle closed, the PA will stay with the subject in the closed room while it is being vented for at least 10 minutes. The study design of parallel groups is being used instead of the original crossover design that was planned.

ElSohy Laboratories, Incorporated (ELI) will perform the stability testing. The laboratory is registered with the FDA and the DEA (Manufacturing and Analytical), all the planned analytical

procedures are validated, and the lab has extensive experience with the drug substance (CBD extract) and with a very similar drug product to ours. Controls for both CBD and THC content are used. The stability testing will be done in real time.

The shelf life will be determined by the testing described below. The final drug product will be stored at room temperature, 25°C.

The microbial testing for the final drug product will be carried out according to UPS 61 (total aerobic microbial count and total combined yeast/mold count) and USP 62 (for salmonella and E. coli), and the specification and acceptance criteria will be the same as recommended in USP <111> (microbiological examination of non-sterile products: Acceptance Criteria for Pharmaceutical Preparations and Substances for Pharmaceutical Use for non-sterile, non-aqueous products with oral administration). This will be the same for the product and placebo. Microbial Specifications:

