- Route of Administration: Nonaqueous preparations for oral use.
- Total Aerobic Microbial Count:<103 cfu/mL •
- Total Combined Yeasts/Molds Count: <102 cfu/mL
- Specified Microorganism(s): Absence of Escherichia coli (1 g or 1 mL)

The CBD extract will be shipped and stored frozen. The final drug product will be prepared within 24 hours of being given to the subject. Once prepared it will be kept at room temperature. The subject will take home the final drug product in 60 ml amber bottles and take it orally for up to 20 days. The stability study will be carried out only at room temperature at the following time points: 0, 1 week, 2 weeks, 3 weeks, 1 month, 2 months, and 3 months. Duplicate analyses will be performed at each time point. Microbial testing will be carried out at the 0 time point for both drug product and placebo and again at the end of one month to show that no change in bioburden occurred during the one month storage at room temperature.

Three manufacturing batches will be prepared (validation lots). These will be subjected to analysis to show consistency of the manufacturing process.

The analytical specification will be that the analytical value should be within 10% of the nominal concentration (i.e. 100 mg CBD/ml should analyze for 90-110 mg/ml). The analytical method is validated for Linearity, LOD, LOQ, accuracy and precision for both CBD and THC.

The specification for the drug product will be:

Appearance: Greenish-yellowish brown, oily solution

Potency: CBD Concentration = 100 mg/mL = 10% solution;  $\pm 10\%$  variation in measured potency (90 to 110 mg/mL) is allowed due to manufacturing and analytical variation. Other Cannabinoids:

- THC not greater than 5 mg/mL (0.5% solution)
- CBD:THC ratio not less than 20:1

We will provide the FDA with a final report with statistical analysis.

We will prepare oral solution of 100 mg/ml CBD (10% CBD) and 3.31 mg/ml THC (0.33% THC) in 60 ml capacity amber glass bottles.

Each bottle will have 30 or 40 mL depending on how much the subject weighs.

- 30 mL CBD Cannabis extract oral solution filled: Each bottle will have 5055 mg of extract placed in it (3000 mg CBD), filled to 30 mL mark with sesame oil.
- 40 mL CBD Cannabis extract oral solution filled: Each bottle will have 6740 mg of extract placed in it (4000 mg CBD), filled to 40 mL mark with sesame oil.

[figure not shown]
Dosage Form and Strength

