# C.3 Randomization and drug dispensation:

Patients who consent will be stratified by age (40-60 and 61-80) and disease severity (H&Y 1-2.5, 3-5) and divided into blocks of a few patients each, depending on order of recruitment. Equal numbers from each block will be assigned to CBD or placebo group in random order.

[name], the PI, will obtain an amended DEA Schedule 1 license prior to the shipment of the study drug and all procedures of drug handling will be according to DEA specifications and protocol provided by University of Mississippi researchers. Briefly, designated study personnel will receive the study drug, do the formulation procedure, store it, measure and label it. The PI or PharmDs will dispense to the participant.

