# **Un-blinding procedures:**

The identity of the treatment assigned to individual participants can be revealed in an emergency only. The PI is responsible for ensuring that the instructions on how to request un-blinding of treatment are stored safely, that their location is known, and that access is readily available to the relevant staff in case of an emergency. [name], the statistician will provide the information when un-blinding is requested by the PI. As a back-up, [name] will provide a file of sealed envelopes to the PI, which is kept in a locked file in her office. The location is known to the PI, sub-I, and coordinator. A sealed envelope coded with each participant number is provided. In the event that [name] is not available to provide break the blind the PI and designated staff can do so. A participant's treatment assignment should only be un-blinded when knowledge of the treatment is essential for the safety of the participant. Un-blinding for any other reason will be considered a protocol deviation.

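### C.2 lets the PI dilute the active extract, which contradicts its own limit on who sees the study drug and does not fit C.4, where the PI appears to be blinded

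*Combined protocol and SAP*

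**What the plan says.** **Formulation (C.2).** The extract arrives as a thick liquid and is diluted with sesame oil. On who does this: "This procedure will be done by the PharmDs ([name], [name], and [name] as a consultant) or PI". For the comparator: "The placebo will be made by the study Pharm Ds from USP grade sesame oil and food coloring". The paragraph admits that placebo may differ a little in look or taste and offers this as one of its safeguards: "the only study personnel to see the actual study drug will be the unblinded PharmD and the blinded CTRC PA". Later in C.2, active bottles hold 30 or 40 mL according to the participant's weight, and "The final drug product will be prepared within 24 hours of being given to the subject".

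**Handling (C.3).** "designated study personnel will receive the study drug, do the formulation procedure, store it, measure and label it". C.3 also allows either the PI or the PharmDs to hand the product to the participant.

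**Blinding (C.4).** Participants and all personnel are blinded apart from a short list of people, whose names are removed from the public copy. Assignment may be revealed only in an emergency: "the statistician will provide the information when un-blinding is requested by the PI". Sealed envelopes are the back-up, and any other un-blinding counts as a protocol deviation.

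**Timing.** C.1 says: "Study drug is dispensed at the baseline visit". The Visit 2 text under Procedures at each visit says: "study drug dispensing is done and, if appropriate, randomization".

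**Rating.** The primary outcome is the change in MDS-UPDRS Part III, which section IV.A says the rater completes. The staff column of Appendix 6 gives the PI and the study subject for the MDS-UPDRS at baseline and at the 2.5 mg/kg/day visit.

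**The concern.** The blind in this trial rests partly on keeping the product out of sight, because the protocol does not expect a perfect match between active and placebo. A sentence that lets the PI handle the active product undoes that safeguard for any participant whose bottle the PI makes. Part III is a clinical examination scored by a person. If the same individual prepared the CBD bottle and scored the examination, the primary comparison would include ratings made by someone who probably knew the assignment. Judgements of whether an adverse event is related to the drug, which C.6 gives to the Investigator, would be exposed in the same way.

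**Working it through.** No arithmetic applies. The check sets the passages against each other.

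1. **C.2 against itself.** The dilution sentence names the PI as an alternative to the PharmDs. The safeguard sentence names two roles as the only ones that see the drug, and the PI is neither. Dilution means placing extract in a bottle and filling to a mark with oil, which cannot be done unseen. If the PI uses the permission, the safeguard sentence is false. This step depends on roles only, so the removed names do not affect it.

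2. **C.2 against C.4.** The list of people excepted from blinding cannot be read, so it does not settle the PI's status. The un-blinding procedure nearly does: the PI requests the code from the statistician, and the envelopes in the PI's office are sealed. A PI who was meant to know assignments would need neither. The PI's blinded status is therefore a strong inference, not an explicit statement.

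3. **Does C.3 resolve it?** No. It leaves formulation to *designated study personnel* without saying who they are.

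4. **What would a PI who dilutes learn?** Placebo is assigned to the PharmDs alone, so the PI's permission covers active product only. Bottles are sized to the participant's weight, made within 24 hours of hand-over and dispensed at baseline. That describes bottles made for individuals, so making one would probably reveal CBD. It is not certain, for two reasons. There are only two fill sizes. Randomization is also at baseline, and the documents do not say whether preparation comes before or after it. PI work on the three validation lots in C.2 would reveal nothing about any participant.

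5. **Route to the primary outcome.** The methods text does not name the MDS-UPDRS rater. Appendix 6 lists the PI at the two visits that form the change score, and C.2 asks for the same assessor at each visit where practical. Appendix 6 also lists the PI for the Clinical Global Impression.

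6. **Size.** A figure would need the share of CBD participants whose bottle the PI made and the amount by which a knowing rater would shift the score. The documents give neither, so none is derived.

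**The case against.** The best reply is that this is one loose phrase in an otherwise blinded design. It is a permission, the PharmDs are named first, and it may be left over from other text. C.2 restricts sight of the drug, C.4 blinds everyone outside a short list, and C.4 treats non-emergency un-blinding as a deviation. Together these largely forbid a PI who formulates from going on to rate.

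That reply is right on one matter. A reader might infer that nothing in the protocol stops a formulator from rating. The documents do not support that: the bar exists in general form, and what is missing is an explicit rule by role.

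It is also fair that the path to bias has several links. The permission must be used, the bottle must be identifiable to a participant already assigned to CBD, and the PI must then be the rater. Appendix 6 is the only source for the last link. It is a visit-duration table and still carries a liver function visit that is not among the five visits in C.1. Sub-investigators also exist.

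What does not fall is the contradiction inside C.2, which needs none of these links. The general rules in C.4 do not cure it either, since C.2 expressly allows an act that C.4 could class as a deviation.

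**Conclusion.** C.2 contradicts itself, and that is certain on the text. The misfit with C.4 is a strong inference, limited by the removed names. That preparing a bottle would reveal CBD is probable. Whether the permission would be used is unknown, and the size of any bias cannot be derived. Severity is minor to should-fix: the harm is conditional, but it falls on a rater-scored primary outcome and the repair is small.

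Three stronger readings should be resisted.

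- A reader might infer that the PI is planned to be unblinded or that the trial is not double-blind. The text gives an option, not a plan, and C.4 points the other way.
- A reader might want an inflated type I error rate. Any such figure would rest on an assumed rating bias and an assumed share of participants.
- A reader might object to the PI dispensing, or see a clash between the physician assistant instructing the participant in C.2 and the PI in the dispensing row of Appendix 6. Handing over a closed opaque bottle is compatible with the blind, and instruction at supervised dosing and instruction at dispensing can both occur.

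**What to change.** Make three wording changes.

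- **C.2:** delete *or PI* from the sentence on who performs the dilution.
- **C.3:** for formulation, have *designated study personnel* refer to the unblinded PharmDs.
- **C.4:** state that anyone who prepares study drug, active or placebo, is unblinded and does no outcome rating and no investigator judgement of adverse events. Both products must be covered, because someone who makes a participant's placebo bottle learns the assignment just as surely.

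The C.4 rule should apply by person. Changing the rater only for participants whose bottle a given person made could itself signal the assignment.

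**Cost.** No added staff, since the PharmDs are already authorised to formulate both products. The trial loses the PI as back-up for formulation. Before the edit, the sponsor should confirm that it is consistent with drug handling under the PI's Schedule 1 license, which C.2 and C.3 mention.

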## **IV. Research Methods**

#### A. Outcome Measure(s):

**Primary Specific Aim:** To evaluate the efficacy of CBD on motor symptoms in PD. **Primary Outcome Measures:** Change of MDS-UPDRS Part III (motor examination) from baseline to the end of 2.5 mg/kg/day of CBD. MDS-UPDRS Part III assesses the motor signs of PD. **Secondary Specific Aim:** To examine safety and tolerability of CBD and the effect of CBD on severity and duration of tremor, night-time sleep, rigidity, emotional dyscontrol, anxiety, and pain in PD.

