photography) will be done. Alertness test (Stanford Sleepiness Scale) will be done before and three hours after the first dosing was administered at clinic. Tremor evaluations reviewed. Home diary is also dispensed. Participants will pick up PSG equipment and home sleep test instruction and do the home sleep test for up to 14 to three nights before the baseline visit. Participants will complete Morning Daytime Dysfunction questionnaire and sleep diary on the morning after the sleep test. PSG equipment and data collected before or at this visit. Participants take the first dose and are instructed on how to take the medication and how to fill out the diary at home. Participants will be monitored for 2 hours and vital signs and orthostatic blood pressures will be checked at one hour after taking the study drug. Participants are also told to bring in empty, partially used, and unused bottles of study drug at next clinical visit. Participants will be told not to take the study drug on the day of the next visit, as they will take it upon arrival under instruction by study staff. Participants will be given two urine cups, 100 mL each, and will be instructed to collect their urine the morning of the 1.25 mg/kg/day assessment visit. They are asked to fill each cup at least three-quarters full, if possible, and to bring them to the visit (no refrigeration needed). Participants are instructed to measure their tremors at home for three days prior to each dose assessment visit.

Part of the above procedures can be done remotely through Zoom or other HIPAA-compliant platform, between screening and onsite baseline visit: Eligibility confirmation, medical history, concomitant medications collection, NMSS, OABSS, Anxiety short form, Depression short form, SCOPA-Sleep, ISI, DBAS-16, Pittsburgh Sleep Quality Index, Dermatology Intake Form, DLQI, Alertness test, RBDSQ, C-SSRS, IRLS, Fatigue severity scale, Pain intensity and interference short form, PDQ-39, EQ-5D.

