Visit 3 (3-4 days, 1.25 mg/kg/day) and Visit 4 (14 (+4) days, 2.5 mg/kg/day), dose assessment visits: On the morning of the visits, participants will collect their urine and bring it to the visits. Study coordinator will collect and store the urine cups in a -80°C freezer until shipment for urinary CBD and metabolites test. Concomitant medications, change in medical history, vital signs, orthostatic blood pressures, complete physical exam, detailed neurological exam, MDS-UPDRS, UDysRS, H&Y rating, tremor constancy and amplitude, NMSS, TUG, Anxiety short form, Depression short form, Emotional and behavioral dyscontrol short form, Fatigue Severity Scale, Pain Intensity and Interference short form, MoCA, RBDSQ, QUIP-RS, C-SSRS, NPI, SCOPA-sleep, ISI, DBAS-16, Pittsburgh Sleep Quality Index, IRLS, OABSS, EQ-5D, PDQ-39, CGI, PGI, blood draw for safety labs (hematology, Complete Metabolic Profile and Liver Function Tests) and blood cannabis analysis, urinalysis, ECG, and urine pregnancy test are done. Study drug compliance check, adverse event check and blinding assessment are done. Participants will take their study drug upon their arrival to the clinic and record the taking time. Blood is drawn for cannabis testing and safety labs three hours after the dose. Participants will be monitored and vital signs and orthostatic blood pressures will be checked at one and three hours (2.5 mg/kg/day dose assessment visit) after taking the study drug. Home diary is collected and reviewed. Urine cups dispensed. In addition to the procedures above, for Visit 3 (3-4 days, 1.25 mg/kg/day), participants are told to bring in empty, partially used, and unused bottles of study drug at next clinical visit. Participants will be told not to take the study drug on the day of the next visit, as they will take it upon arrival under instruction by study staff. Participants are instructed to measure their tremors at home for three days prior to 2.5 mg/kg/day dose assessment visit. Participants will be given the questionnaires of SCOPA-sleep, Anxiety short form, Depression short form, Emotional and behavioral dyscontrol short form, EQ-5D-5L, C-SSRS. Study staff will call the participants on the 3rd to 5th day on 2.5 mg/kg/day to remind them to complete the questionnaires and bring it in at next clinic visit.

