Pre-dilution dosage unit: CBD Cannabis Extract (depending on the subject's weight it will contain either 3 or 4 gms CBD) Diluted Unit: CBD Cannabis Oral Solution (100mg/ml CBD)

The FDA has approved our IND. The DEA has approved the PI's amended DEA Schedule 1 license. Participants will be given bottles with 30/40 ml of study drug, at concentration of 100 mg/ml CBD or placebo and instructed how to take it. The study drug is best taken fasted, as food will increase Cmax and delay Tmax. The study drug could be taken with a small amount of food as needed if the participants experience nausea. The study drug will be taken orally, started at 1.25 mg/kg/day of CBD, once daily in the morning for four days, then increased to 2.5 mg/kg/day, twice daily at standard times, with a minimum of six hours apart (Figure 2 dosing plan). Participants are instructed to take it before breakfast (30 to 60 minutes) and the same before dinner. Participants are instructed not to drink grapefruit for seven days prior to the first dose of study medication and during the rest of the study.

The study drug is taken as normal on the mornings of assessments. As far as practical, the same assessor carries out assessments at each visit. Assessment data are stored and not made available at subsequent visits.

Figure 2: Dosing plan.

Legend: V: Visit. D: Day. QD: once a day. BID: twice a day. PC: Phone call.

V1: -28 to -1 day. Screening visit.

V2: Day 1, Baseline visit: The first day of CBD 1.25 mg/kg/day. 4 weeks within screening visit.

V3: Day 3/4, 1.25 mg/kg/day dose assessment visit: The third to fourth day of CBD 1.25 mg/kg/day. PC: Day 7-9, Questionnaire survey reminder phone call. The third to fifth day of CBD 2.5 mg/kg/day.

V4: Day 14, 2.5 mg/kg/day Dose Assessment Visit: The 10th day of CBD 2.5 mg/kg/day.

V5: Day 28, Safety follow up visit, 2 weeks after stopping study drug.

Participants take their routine anti-PD medication on the day of their clinical visit, and when ON (PD medications are working) the testing is done.

CBD and metabolite levels will be measurements: Blood CBD and metabolite levels will be measured at screening visit, each dose assessment visit, and safety follow up visit. Urinary CBD and metabolites levels will be tested at dose assessment visits and safety follow up visit. Potential drug-drug interactions:

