# 4. Liver function monitoring visit

Liver Function monitoring visit	Time	Note
Medical History	2	PRA
Concomitant Medications	2	PRA
Adverse Events (b) and drug abuse related AEs	3	PRA
Anxiety short form	2	Study subject
Depression short form	2	Study subject
Emotional and behavioral dyscontrol short form	2	Study subject
SCOPA-sleep	4	Study subject
EQ-5D	2	Study subject
C-SSRS	2	PRA
Vitals	5	PRA
Blood draw for liver function tests	10	CTRC
Total visiting time	36	0.5 hours

2.5 mg/kg/day Dose assessment visit	Time	Note
Vital Signs, orthostatic BP	10	PRA, Begore taking study drug
Taking study drug in clinic	2	Study subject
Cognitive assessment battery	60	PRA
Vital Signs, orthostatic BP	10	PRA, one hours after taking study drug
Medical History	2	PI, PRA
Concomitant Medications	2	PI, PRA
Adverse Events and drug abuse related AEs Withdrawal AEs and liver function related AEs	3	PI, PRA
Complete Physical Exam	10	PI
Neurological exam	10	PI
QUIP-RS	5	PI
CGI	1	PI
MDS-UPDRS (all 4 parts), H&Y, Schwab & England Activities of Daily Living Scale	30	PI, Study subject
Unified Dyskinesia Rating Scale (UDysRS)	5	PI, Study subject
MOCA	10	PRA
TUG	5	PRA
NMSS	10	PRA
Home diary collection and review	2	PRA
Tremor constancy and amplitude measure (k)	5	PRA, 2 hours after taking study drug
PSG equipment and data collected (u)	2	PRA
Blinding assessment	1	PRA
Study drug compliance check	2	PRA
C-SSRS	2	PRA
RBDSQ	2	PRA
NPI	5	
Anxiety short form	2	Study subject
Depression short form	2	Study subject
Emotional and behavioral dyscontrol short form	2	Study subject
SCOPA-sleep	5	Study subject
Insomnia Severity Index (ISI)	2	Study subject
Modified Dysfunctional Beliefs and Attitudes about Sleep Questionnaire (DBAS-16)	3	Study subject
Pittsburgh Sleep Quality Index	3	Study subject
IRLS	2	Study subject
Fatigue severity scale	3	Study subject

5. 2.5 mg/kg/day Dose assessment visit

Pain intensity and interference short form	2	Study subject
Bladder function-OABSS	3	Study subject
PDQ-39	5	Study subject
EQ-5D	2	Study subject
PGI-I	1	Study subject
PGI-C	1	Study subject
Urinalysis, pregnancy test if applicable	5	PRA
Urinary collected for CBD and metabolites levels test	2	PRA
Take picture of central face	5	PRA, Study subject
ECG (12-LEAD)	10	CTRC
Blood draw for Hematology, CMP, cannabis test	10	CTRC, 3 hours after taking study drug
Vital Signs, orthostatic BP	10	PRA, 3 hours after taking study drug
Total visiting time	275	4 hours

6.Safety follow up visit		
Safety follow up visit	Time	Note

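### Section C.2 contradicts the visit procedures and Appendices 1 and 6 on when the visit-day dose is taken, and no post-dose window is set for the primary MDS-UPDRS Part III

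*Combined protocol and SAP*

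**What the plan says.** Section IV.C.2 (Study Drug) states that "The study drug is taken as normal on the mornings of assessments". A few sentences earlier it describes ordinary dosing: "Participants are instructed to take it before breakfast (30 to 60 minutes) and the same before dinner". In the twice-daily phase, doses are taken "twice daily at standard times, with a minimum of six hours apart".

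Section IV.C.1 (Procedures at each visit) gives a different rule. At the baseline visit, looking ahead to Visit 3, and again at Visit 3, looking ahead to Visit 4: "Participants will be told not to take the study drug on the day of the next visit, as they will take it upon arrival". For Visits 3 and 4 themselves: "Participants will take their study drug upon their arrival to the clinic and record the taking time". Later in the same visit: "Blood is drawn for cannabis testing and safety labs three hours after the dose".

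The appendices side with the visit procedures. The Day 14 column of Appendix 1 has the dose taken on arrival. Appendix 6 lists "Taking study drug in clinic" at both dose assessment visits, after the pre-dose vital signs.

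The primary outcome (section IV.A) is "Change of MDS-UPDRS Part III (motor examination) from baseline to the end of 2.5 mg/kg/day of CBD". No time after study drug is attached to it. The only timing condition on testing, in C.2, is that the participant's usual anti-Parkinson medication is working.

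**The concern.** C.2 is where a reader looks for how study drug is taken. Its assessment-morning sentence follows closely on the before-breakfast rule, so the natural reading is a dose at home. The visit procedures exclude that.

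Three things depend on which text is followed:

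- **Post-dose measurements.** Vital signs, tremor and the blood draw all have set times relative to the clinic dose. Section III expects the peak blood level at about three hours, and C.2 notes that food raises Cmax and delays Tmax. When and how the dose was taken therefore affects what these measurements mean.
- **Spacing of doses.** The protocol wants at least six hours between doses, and Section III gives the reason: to limit overlap of the THC effect. A home dose repeated on arrival would break that spacing.
- **The primary rating.** Visit 4 supplies the MDS-UPDRS Part III. Its position after the study-drug dose is not set in either text.

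**Working it through.** **1. The texts side by side**

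| Place | Visit-day dose |
|---|---|
| C.2 | Ordinary morning dosing, i.e. 30 to 60 minutes before breakfast |
| C.1, Visit 2 text (for Visit 3) | Not before the visit; on arrival, under staff instruction |
| C.1, Visit 3 text (for Visit 4) | The same |
| C.1, Visits 3 and 4 | On arrival, time recorded |
| Appendix 1, Day 14 | On arrival at clinic |
| Appendix 6, items 3 and 5 | In clinic, between pre-dose and one-hour vital signs |

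C.2 stands alone against the rest.

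**2. What is timed from the clinic dose** (C.1; Appendix 1, footnotes k, n, o, p)

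- Vital signs: before dosing and at 1 hour, plus 3 hours at Visit 4.
- Tremor: 2 hours.
- Blood draw: 3 hours.

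Suppose the dose is taken at home *h* hours before arrival, is not repeated, and staff count from arrival. The tremor measure then falls at 2 + *h* hours and the blood draw at 3 + *h* hours, and the pre-dose vital signs are no longer pre-dose. The documents give no value for *h*.

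**3. Size of the foreseeable error: a home dose plus a clinic dose**

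Inputs from Section III: 1.25 mg/kg CBD and 0.041 mg/kg THC per dose; average weight 84 kg; about 3.3 mg THC per dose as the protocol rounds it; approximate threshold 5 mg THC.

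- CBD at 84 kg: 2 × 1.25 × 84 = 210 mg.
- THC at 84 kg: 2 × 0.041 × 84 = 6.9 mg, or 2 × 3.3 = 6.6 mg with the rounded figure.
- THC at 60 kg (assumed): 2 × 0.041 × 60 = 4.9 mg.
- THC at 100 kg (assumed): 2 × 0.041 × 100 = 8.2 mg.
- Weight at which two doses reach 5 mg: 5 / (2 × 0.041) = about 61 kg.

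The six-hour minimum is stated for the twice-daily phase, so the breach arises at Visit 4. At Visit 3 the same error would put a second dose into a once-daily phase.

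**4. Dose to MDS-UPDRS in Appendix 6**

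Minutes of procedures listed between clinic dosing and MDS-UPDRS:

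- Visit 3: 10 + 2 + 2 + 2 + 3 + 10 + 10 + 5 + 1 = 45.
- Visit 4: 60 + 10 + 2 + 2 + 3 + 10 + 10 + 5 + 1 = 103. The added item is the 60-minute cognitive battery.

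These are listed minutes, not clock times, and the order is not stated to be binding. At Visit 3 the first item after dosing is the one-hour vital signs. If staff wait for it before going on, MDS-UPDRS would start at about 60 + 45 = 105 minutes. The interval therefore depends on how the list is worked.

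**The case against.** The strongest defence is that C.2 makes a general statement about conduct, next to remarks on assessors and data storage. It can be read as saying only that study drug is not withheld on assessment days, with the visit procedures supplying place and time. Participants act on what staff tell them, and the only visit-day instruction worded to them is to wait.

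Much of this stands, and it rules out several stronger readings that a reader might infer:

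- **That participants are given two opposite instructions.** The documents do not show this; the C.2 sentence is not addressed to them.
- **That dose timing at the primary assessment is undefined.** On-arrival dosing with a recorded time is set out in several consistent places. What is unset is the interval from that dose to the rating, and deleting the C.2 sentence would leave that gap unchanged.
- **That the plan leads to double dosing.** No passage directs two morning doses. A participant would have to act against the instruction and staff would have to miss it. The diary and compliance checks at these visits might catch it, though the protocol does not say that they precede dosing. The 5 mg figure is itself approximate, and Section III says it varies with many factors.
- **That the drug level can no longer be related to the motor score.** The dose time is recorded, the draw is fixed at three hours, and section F plans no analysis of level against MDS-UPDRS.

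One may add that Section II gives an oral CBD half-life of 2 to 5 days, so a few hours may matter less by Day 14. That tempers the secondary point. It does not help the 1-, 2- and 3-hour measurements, which the protocol chose to time from the dose.

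The benign reading of C.2 does not remove the need for a correction, because the section itself says what ordinary morning dosing is.

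**Conclusion.** The contradiction is real. C.2, read plainly, is incompatible with the visit procedures, Appendix 1 (Day 14) and Appendix 6. The consequence is confined to mistimed post-dose measurements if staff follow C.2, and to a foreseeable dosing error that would breach the six-hour minimum at Visit 4. The size of that error is 6.6 to 6.9 mg THC at 84 kg, and 4.9 to 8.2 mg over assumed weights of 60 to 100 kg. It rests on the protocol's per-kilogram doses and on both doses being taken the same morning.

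The missing dose-to-MDS-UPDRS interval is a separate, lesser gap. A reader might infer that it biases the primary comparison. The documents do not support that: the timing rules are the same in both randomised arms. The expected effects are added variability and some vagueness about which part of the post-dose period is being assessed. The documents give no basis for putting a figure on that variability.

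No view is taken here on which dosing rule is right.

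**What to change.** Reconcile the C.2 sentence with the visit procedures in C.1, Appendix 1 and Appendix 6, so that one visit-day dosing statement stands throughout and participant instructions match it. This costs one line of text.

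Secondarily, state one window from study drug to MDS-UPDRS Part III, the same at Visits 3 and 4, and check that the Appendix 6 running order can meet it. This costs a sentence and possibly a reordering of the visit list. It needs no change to sample size or to the primary test.
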